This is a randomized, double-blind, placebo-controlled, two-arm parallel, single-center study. One hundred subjects (50 in each arm) will be enrolled. Subjects, between the ages 18 and 65, undergoing laparoscopic gastric bypass or sleeve gastrectomy under general anesthesia will be screened for eligibility to participate in the study. Subjects will be screened, recruited and consented during the preadmission visit prior to surgery. Eligible subjects will be randomized to one of the two treatment group in a 1:1 ratio to receive either IV ketamine (0.4mg/kg) or matching placebo. Both men and women will be recruited, and there is no limitation as to racial and ethnic origin.

Participation in the study will not alter the patient's surgical or anesthetic care, post-anesthetic care, or care on the floor. In the PACU, patients, if deemed medically stable by the study physician, will receive either 0.4mg/kg IV ketamine or placebo. All patients will also receive standard post-anesthetic monitoring and care, as well as routine care after transfer out of the PACU. There is no restriction on the use of other analgesics throughout the hospital stay. Patients are followed until the date of discharge, and endpoints (see below) are collected from patient reports as well as from medical charts. During their hospital stay (and once after their discharge from the hospital), patients will fill out five questionnaires which provide estimates of their postoperative pain control, mood and function, and quality of postsurgical recovery.

Patients will be randomized using a block randomization code for assigning 100 subjects to two groups. In Excel we generated 100 random numbers. In the next column we inserted multiple copies of the sequence PCPC where p= "placebo" and c = "control", forming 25 blocks. Then we sorted the random numbers in each 4 subject block, including the assignment letters (P, C) in the sort. The remaining list of Ps and Cs is the randomization.

To check the balance, we then did running counts of the cumulative repeats of "p" and "c" and "p - c". The tally for each totaled 50 and the two groups were always within 2 counts of being perfectly balanced, which met our goal. The list can be extended at will to accommodate screening failures.

Randomization lists will be sent to the pharmacy who will then be able to distribute the study drug/placebo as patients are enrolled and undergoing surgery, and the remainder of the study staff will be blinded.

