Potential subjects will have an initial pre-study screening, conducted by a member of the research team, to determine eligibility for the study. Potential subjects who are non-English speaking will be automatically excluded, because the questionnaires are copyrighted in English only. Subjects who do not have the capacity to consent will not be recruited. All other subjects will be recruited. For any patient who might be illiterate, consents will be read to him or her and witnessed by available staff or family member.

Informed Consent

Eligible patients will be assessed for capacity to give informed consent by a study team member. Medical clearance/status/stability will be addressed by members of the research team. Eligible patients will be invited to participate in the study. A verbal explanation of the study will be given followed by a written consent form. Study staff members are experienced at consenting patients for anesthesiology studies, and they include physicians as well as research associates.

[figure not shown]
Intervention Administration

Ketamine bolus doses of 0.4 mg/kg (by ideal body weight) will be prepared and stored by the Pharmacy staff at Tisch Hospital and will be delivered to the PACU on an on-call basis when required for a study subject. The study drug will be administered in accordance to best practices. Ketamine will be given via intravenous infusion through an IV line established in the PACU. All patients will have an IV line in the PACU as per standard postoperative care protocol after bariatric surgery. If necessary, an additional IV line will be placed by the study team for the infusion of the study drug. The study drug or control will be administered over <60 minutes. The dose for ketamine will be fixed at 0.4 mg/kg (ideal body weight). The staff administering the infusion will have no knowledge whether the agent is drug or saline control. The patient will be monitored in the PACU according to the standard PACU protocol. In addition, the patient will be monitored for any potential side effects of the medication, which include hypertension, tachycardia, nystagmus, perceptual disturbances, confusion, sedation, euphoria, dysphoria, and dizziness. These side effects are uncommon, and a majority of these side effects are expected to resolve shortly after infusion.¹³ Side effects will be documented and treated if necessary as per standard PACU protocol.

Study drug storage

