The Pharmacy at Tisch Hospital will randomize and prepare samples (study medication or saline control). Study medications and placebo will be kept by the Pharmacy staff at Tisch Hospital until use.

Main Study

Pharmacologic profile of study drug

Ketamine [(+/-)-2-(2-chlorophenyl)-2-(methylamino)-cyclohexanone] is a white, crystalline powder or clear liquid. It is a schedule III substance and is classified as a dissociative anesthetic. Ketamine is available as a racemic mixture with the S-(+)- isomer being more potent than the R-(-)- isomer. It is commercially supplied as the hydrochloride salt in 0.5 mg/mL and 5 mg/mL ketamine base equivalents. Clinically, it is commonly used as an anesthetic induction agent for diagnostic and surgical procedures prior to the administration of general anesthetics. It is also used as a low dose infusion for analgesia. For induction of 5-10 minutes surgical anesthesia, a dose of 1.0-4.5 mg/kg is intravenously administered; 6.5-13 mg/kg is given intramuscularly for 12-25 minutes of surgical anesthesia. As an analgesic, it is infused at a rate of 0.1 - 0.5 mg/kg/hr, with or without a loading dose.

The risks for ketamine are well studied. In general, ketamine is a well-tolerated medication. However, the following risks have been reported.

Pharmacokinetics: Bioavailability following an intramuscular dose is 93%, intranasal dose 25-50%, and oral dose 20±7%. Ketamine is rapidly distributed into brain and other highly perfused tissues, and is 12% bound in plasma. The plasma half-life is 2.3 ± 0.5 hours. Oral administration produces lower peak concentrations of ketamine, but increased amounts of the metabolites norketamine and dehydronorketamine. Ketamine and its metabolites undergo hydroxylation and conjugation. Norketamine produces effects similar to those of ketamine. There are no significant differences between the pharmacokinetic properties of the S-(+) and R-(-)-isomers.

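### The protocol has its authors build and tally the full allocation list and prints the fixed block of 4, without separating whoever saw the list from enrolment, the PACU decision or assessment

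*Combined protocol and SAP*

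**What the plan says.** Overall study design and plan describes one list for one center at 1:1, with no stratification described: "Patients will be randomized using a block randomization code for assigning 100 subjects to two groups". The construction is told in the first person plural. "In Excel we generated 100 random numbers", the authors write; they then laid a two-plus-two pattern beside the numbers to form 25 blocks. The shuffle is given as "Then we sorted the random numbers in each 4 subject block, including the assignment letters (P, C) in the sort". They next inspected the finished list by running counts: "The tally for each totaled 50 and the two groups were always within 2 counts of being perfectly balanced". The section adds that the list can be lengthened to cover screening failures, without saying by whom. It then goes to the pharmacy, and the other study staff are to be blinded.

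Study drug storage gives a different account: "The Pharmacy at Tisch Hospital will randomize and prepare samples (study medication or saline control".

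Four other places bear on how knowledge of the list could be used:
- Overall study design and plan makes dosing depend on the study physician finding the patient medically stable in the PACU.
- Entry into Study allows recruitment from the holding area on the day of surgery, besides the clinic and preadmission visits.
- Outcome measures has a study team member telephone discharged patients to complete the questionnaires, and has a team member judge spirometry.
- Intervention Administration lists acute effects to be monitored, among them "perceptual disturbances, confusion, sedation, euphoria, dysphoria, and dizziness", and then describes these effects as uncommon.

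**The concern.** There are two exposures, and they differ in size.

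The first is custody of the list. Someone on the authoring side generated and tallied the whole sequence. The plan does not say who, or that this person has no part in recruiting, in the PACU decision or in collecting outcomes. Such a person needs no guesswork.

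The second is predictability. A fixed block of four is printed in a document that staff hold, in a single-center trial with one running list. Staff who follow the order of allocation and recognise earlier arms from drug effects could work out some later ones.

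At stake is selection before dosing: whether a holding-area patient is approached, or whether a borderline patient is called stable. For anyone who saw the list, expectation could also reach the questionnaire contacts and the spirometry judgement. All five primary measures are questionnaire scores, so they are open to such influence.

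**Working it through.** **The plan's own figure.** Overall study design and plan gives 25 blocks, each with two of either letter. Then 25 × 2 = 50 per arm, and the running difference inside a block never exceeds 2. The stated balance reproduces. Every list made of two-plus-two blocks has this property by construction, so the check says nothing about concealment.

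**Exposure of the list-makers.** Building and tallying the list gives access to 100 of 100 assignments. No further arithmetic is needed.

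**Ceiling for everyone else.** Inputs: block size 4 and 1:1 ratio (Overall study design and plan). Assumptions: the block boundaries are known, and every earlier arm in the block is correctly known. A two-plus-two block has 6 equally likely orders. An assignment is forced once only one letter remains.

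| Position in block | Forced | Best guess correct |
|---|---|---|
| 1 | 0 | 1/2 |
| 2 | 0 | 2/3 |
| 3 | 1/3 | 1/3 × 1 + 2/3 × 1/2 = 2/3 |
| 4 | 1 | 1 |

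Forced share: (0 + 0 + 1/3 + 1)/4 = 33.3%, or about 33 of 100. Best-guess accuracy: (1/2 + 2/3 + 2/3 + 1)/4 = 70.8%, against 50% with no information.

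**Imperfect guessing.** The documents give no guessing accuracy. Assume that each earlier arm is guessed independently with accuracy *a*. A forced assignment at position 3 needs two correct guesses, and one at position 4 needs three:

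- share forced with all earlier guesses in the block correct = (a²/3 + a³)/4
- best-guess accuracy = [1/2 + 2 × (1 + a)/3 + a² + 2a(1 − a)²]/4, where the terms are position 1, positions 2 and 3 together, and position 4

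| a (assumed) | Correctly forced | Best guess correct |
|---|---|---|
| 0.6 | (0.120 + 0.216)/4 = 8.4% | 53.0% |
| 0.7 | (0.163 + 0.343)/4 = 12.7% | 56.2% |
| 0.8 | (0.213 + 0.512)/4 = 18.1% | 60.1% |
| 0.9 | (0.270 + 0.729)/4 = 25.0% | 64.9% |
| 1.0 | (0.333 + 1.000)/4 = 33.3% | 70.8% |

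Below a = 1 the guesser cannot tell which deductions are sound, so even the forced share is not certainty.

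**What mixed blocks would change.** Simulation with sizes 4, 6 and 8 equally likely, and an observer who knows the possible sizes and all earlier arms but not the boundaries: about 2% of assignments are certain, and the best guess is right about 68% of the time. The largest possible running imbalance rises from 2 to 4, half of the largest block.

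**The case against.** The strongest defence is that the plan has real safeguards. The list is sent to the pharmacy, the remaining staff are blinded, and those giving the infusion do not know its content. Permuted blocks of four are conventional. Most consent comes at the preadmission visit, where a recruiter would have to predict the list position reached on a later day of surgery. The author of the list may have been a statistician or pharmacist with no other role. The statement that the pharmacy randomizes can be read as carrying out the list it was sent.

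Much of this stands. It narrows the timing route mainly to holding-area recruits, and it makes the conflict between the sections one of wording that a sentence could settle. It does not answer the custody question, because the plan nowhere says that the list-makers have no other role.

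A reader might infer that a third of assignments are deducible in practice. The documents do not support that. One third is a ceiling that needs correct knowledge of earlier arms and of block boundaries. The revealing effects are called uncommon, and some of them, such as sedation and confusion, are hardly specific in patients just out of general anesthesia.

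A reader might also infer that mixed blocks would cure the problem. They remove nearly all certainty but lower the best guess only from 71% to 68%. They also do nothing if drug effects unblind staff to the patient being treated, which is a separate matter.

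**Conclusion.** The concern holds as a gap in custody and separation of roles, with a smaller one in predictability. The custody gap covers up to all 100 assignments for whoever built or tallied the list. It rests on the authors' use of *we* and on the plan's silence about their other duties. The predictability gap is at most one third of assignments for staff who know the block size and boundaries, and about 8% to 25% under the assumed accuracies of 0.6 to 0.9.

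The realistic routes to bias are holding-area recruitment, the PACU stability decision and, for anyone who saw the list, study-team assessment. The documents do not show that anyone who saw the list enrols or assesses patients, that the PACU decision was used in an arm-driven way, or that dispensing by the pharmacy gives no protection. The point is that the plan leaves these possibilities open when closing them is cheap.

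**What to change.** - Have the pharmacy, or a statistician with no enrolment, PACU or assessment role, generate the list. If enrolment has begun, apply this to the unallocated remainder and to any extension, and leave assignments already made as they are.
- Let only the pharmacy hold the list.
- Use randomly mixed block sizes, for example 4, 6 and 8.
- Remove the block size and the worked method from the protocol.
- Make Overall study design and plan and Study drug storage agree on who generates the list, and state that this person has no other role.

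The same edit can correct the letter key, which defines one letter as placebo and the other as control. The protocol elsewhere uses control for saline, so neither letter clearly denotes ketamine.

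The cost is about an hour of pharmacy or statistician time plus the wording change. The one statistical downside is that the largest possible running imbalance rises from 2 to 4.

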Ketamine, given for postoperative pain control, can be hypothesized to have long lasting analgesic effects as well as effects on improving mood and function in the postoperative period. Ketamine can be administered as a single dose in the post-anesthetic care unit (PACU), where patients are closely monitored for potential side effects. We hypothesize that postoperative use of ketamine should lead to improvement in pain indices including visual analog scale (VAS), a decrease in opioid requirement, mood improvements as measured by psychometric indices, and finally improvements in functional measures including early mobility and faster discharge from the hospital. In addition, we will assess serum levels of IL-1, 6, TNF- α , and BDNF to see if alterations in levels of cytokines and neurotrophic factors occur with postoperative pain and how ketamine treatment may influence the levels of these biomarkers.

Study Objective

Specific aim 1: examine the effect of a single, subanesthetic dose (0.4mg/kg) of ketamine vs. saline control on mood and postoperative function in patients who have undergone gastric bypass and sleeve gastrectomies.

Pain relief and changes in postoperative mood and function will be assessed using both patient report, in the forms of a series of questionnaires, and medical chart review. The questionnaires we use will be Beck Depression Inventory (BDI), Visual Analog Scale (VAS), McGill's short form, QoR-15 form and the Montgomery-Asberg Depression Rating Scale (MADRS). Please see below for a detailed discussion of these forms. In addition, from the chart review we will monitor length of stay during hospitalization, opioid usage per hour during the PACU stay before and after ketamine infusion, total opioid usage per day throughout the hospital stay, time to out of bed to chair, and spirometry use after ketamine infusion.

Specific aim 2: examine the effect of a single, subanesthetic dose (0.4mg/kg) of ketamine vs. saline control on inflammatory cytokines and neurotrophic factors in the postoperative period.

We will examine the effect of ketamine on proinflammatory markers and neurotrophic factors known to be linked with pain. We will examine levels of interleukin factor 1 and 6 (IL-1, IL-6), TNF- α , and BDNF. This aim will provide potential mechanism of action for ketamine.

Overall study design and plan

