An additional component of the study, which is entirely optional, is to obtain patient serum samples (about two teaspoons) in the operating room and 15 minutes and 4 hours after ketamine infusion. We will use these samples to assess levels of IL-1, IL-6, TNF- α , and BDNF, which are markers for pain. In addition, with patient consent, we will also store serum samples for future research use to measure other cytokines and neurotrophic factors and molecular markers associated with pain and depression.

Study site: Tisch Hospital

Outcome measures

Primary outcome measure: scores on the following questionnaires: 1) The Beck Depression Inventory (BDI); 2) Visual Analog Scale (VAS) score; 3) McGill's short form; 4) QoR-15 form; and 5) Montgomery-Asberg Depression Rating Scale (MADRS). The BDI and MADRS provide assessments for mood and function, VAS and McGill's assess pain, and QoR-15 assesses patient's overall satisfaction with postoperative recovery.

After consent is achieved in the pre-admission clinic prior to surgery, patients will be asked to fill out BDI, MADRS and QoR-15 forms to establish baseline scores. The BDI, MADRS will be filled out on postoperative days (POD) 0 after the infusion of ketamine, and BDI, MADRS and QoR-15 forms will be repeated on POD1, 2 and 7. McGill's short form will be filled out prior to discharge from the PACU and on POD 1, 2 and 7. VAS will be filled prior to PACU discharge, and every day while patient is in the hospital and on POD 7. VAS is a routine part of hospital care and will be administered daily whether a patient is enrolled in the study or not. If a patient has been discharged prior to POD2 or 7 (patients typically are discharged on POD2 or 3 in our practice), then a member of the study team will contact the patient by telephone to fill out these questionnaires.

Secondary outcome measures: 1) length of stay during hospitalization; 2) opioid usage per hour during the PACU stay before and after ketamine infusion; 3) opioid usage per day throughout the hospital stay; 4) time to out of bed to chair (OOB); 5) spirometry use 4 hours after the termination of ketamine infusion; 5) anti-emetic use in the PACU.

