Sample Size Justification: Previous studies on the antidepressant effects of ketamine on depressed patients typically yield a mean difference in psychometric measures of 40%, with a standard deviation of roughly 40% as well. Power analysis yields $n = 50$ patients in each arm. This will allow for us to detect a true difference in the mean value of our outcome variable of $\pm 22.5\%$ with a probability (power) of 0.8. The type I error probability associated with this test of the null hypothesis that the population means of the ketamine versus control groups are equal is 0.05.

Statistical Analysis: For this study, descriptive statistics will be performed for all data and subgroups as needed:

- 1) Outcome tests (see above), N (%) for each category, showing absolute values, absolute

and percent differences, stratified by treatment etc.

- 2) Demographics showing continuous parameters (age, height, weight, etc.) as mean + SD; categorical parameters, as N (%); all also stratified by treatment.

Analysis of variance (ANOVA) test with repeated measures will be performed to determine within-patient effects (time) and between patient effects (treatment) on outcome measures. Pearson correlation will be used to assess relationships between continuous variables, and Spearman's Rho will be used for ranked data. For non-normally distributed, the Kruskal-Wallis test will be used for global significance, and Mann Whitney for subsequent pairwise comparisons.

Exploratory analysis will fit continuous (VAS score, length of stay in the hospital) and categorical (ordinal outcome data) to a Logistic Regression model which predicts the treatment bivariate (IV ketamine or placebo).

Interim Data analysis: An interim data analysis will be performed after a total of 50 patients have completed the study. An analysis of primary and secondary endpoints will be analyzed, and if the primary endpoints are met, we will opt to terminate the study.

DATA SAFETY AND MONITORING PLAN

Timeline

- 1) Estimated start date: Sept 1, 2013
- 2) Estimated time for start-up: 2 months
- 3) Time allotted for enrollment: 2 years
- 4) Estimated study end date: August 30, 2015

Data acquisition and management

The research material obtained from human subjects in this proposed study will be collected solely for research purposes. It will be as follows:

- a. *Clinical information* obtained by medical history, questionnaires and interviews.

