Sample Size Justification: Previous studies on the antidepressant effects of ketamine on depressed patients typically yield a mean difference in psychometric measures of 40%, with a standard deviation of roughly 40% as well. Power analysis yields $n = 50$ patients in each arm. This will allow for us to detect a true difference in the mean value of our outcome variable of $\pm 22.5\%$ with a probability (power) of 0.8. The type I error probability associated with this test of the null hypothesis that the population means of the ketamine versus control groups are equal is 0.05.

Statistical Analysis

For this study, descriptive statistics will be performed for all data and subgroups as needed:

- 1) Outcome tests (see above), N (%) for each category, showing absolute values, absolute and percent differences, stratified by treatment etc.
- 2) Demographics showing continuous parameters (age, height, weight, etc.) as mean + SD; categorical parameters, as N (%); all also stratified by treatment.

Analysis of variance (ANOVA) test with repeated measures will be performed to determine within-patient effects (time) and between patient effects (treatment) on outcome measures. Pearson correlation will be used to assess relationships between continuous variables, and Spearman's Rho will be used for ranked data. For non-normally distributed data, the Kruskal-Wallis test will be used for global significance and Mann Whitney for subsequent pairwise comparisons.

Exploratory analysis will fit continuous (VAS score, length of stay in the hospital) and categorical (ordinal outcome data) to a Logistic Regression model which predicts the treatment bivariate (IV ketamine or placebo).

Interim Data analysis

An interim data analysis will be performed after a total of 50 patients have completed the study.

An analysis of primary and secondary endpoints will be analyzed, and if the primary endpoints are met, we will opt to terminate the study.

Data Safety and Monitoring Board (DSMB)

In addition to the PI, [name], an independent patient safety DSMB panel will also review study documents and safety data on a routine basis. This board will meet once every three months, and more frequently as needed. In addition, the board will meet with study coordinator and assistant after a total of 50 patients have completed the study to perform an interim analysis. This board will include the additional following members from the department of anesthesiology.

1. [name]
2. [name]

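### Five unranked primary questionnaires have no success or multiplicity rule, while the stated 0.05 and 0.8 belong to one test of one unnamed outcome

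*Combined protocol and SAP*

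**What the plan says.** - **Outcome measures.** "Primary outcome measure: scores on the following questionnaires" is followed by BDI, VAS, McGill's short form, QoR-15 and MADRS in one numbered list. They cover different domains: "The BDI and MADRS provide assessments for mood and function", two others assess pain, and QoR-15 assesses satisfaction with recovery.
- **Timing.** Each scale is taken several times. BDI and MADRS are completed on the day of surgery after the infusion, and then "BDI, MADRS and QoR-15 forms will be repeated on POD1, 2 and 7". McGill's short form has four post-dose assessments. VAS is taken before PACU discharge, daily in hospital and on day 7. No primary day is chosen.
- **Study Objective, Specific aim 1.** The comparison is of ketamine "vs. saline control on mood and postoperative function", and the text goes on to mention pain relief.
- **Sample Size Justification** (given twice, in the same words). The basis is: "Previous studies on the antidepressant effects of ketamine on depressed patients typically yield a mean difference in psychometric measures of 40"%, with an SD of about 40% as well. Fifty per arm are said to "detect a true difference in the mean value of our outcome variable of" ±22.5% with power 0.8 and type I error 0.05. The variable is not named.
- **Statistical Analysis.** Repeated-measures ANOVA is to assess "within-patient effects (time) and between patient effects (treatment) on outcome measures". The Kruskal-Wallis and Mann-Whitney tests are the alternative for non-normal data.
- **Interim Data analysis.** After 50 patients, "if the primary endpoints are met, we will opt to terminate the study".

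No section gives a hierarchy, an alpha split, a composite, a co-primary rule or a rule for how many scales must succeed.

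**The concern.** The stated error rate and power describe one test, but the primary outcome set has five members, each measured repeatedly. What makes the trial positive is open in two ways: which scales must succeed, and which ANOVA effect (treatment averaged over visits, treatment by time, or a single day) is decisive. The two natural readings fail differently. If any scale suffices, 0.05 is not the trial's error rate. If all five are needed, 0.8 is not shown to be its power.

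The same undefined condition also decides whether the trial ends at half its planned size. With nothing fixed in advance, the rule could be chosen after the results are seen, and later reporting cannot repair that.

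**Working it through.** **1. Reproduce the plan's figure.** Inputs from Sample Size Justification: difference 22.5%, SD 40%, alpha 0.05 (taken as two-sided because of the ±), power 0.8.

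n per arm = 2 × (1.960 + 0.842)² × (40/22.5)² = 2 × 7.85 × 3.16 = 49.6, so 50.

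With 50 per arm, SE = 40 × √(2/50) = 8.0 and 22.5/8.0 = 2.8125. Power = Φ(2.8125 − 1.960) = 0.803, or 0.795 by the t-test with 98 df. A one-sided test would need only 40. The stated figure is therefore one two-sided test at the full 0.05, with 40% as the SD of the variable tested.

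**2. Assumptions beyond the documents.** One two-sample treatment test per scale. The correlations between scales are not given. I take 0.7 or 0.8 within a domain (BDI with MADRS, VAS with McGill) and 0.3 or 0.5 otherwise. Equal correlations of 0 and 0.9 are the extremes. For power, the true effect is 22.5% on every scale.

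**3. Final analysis, each scale at 0.05** (t-tests, 100,000 simulations per structure). Error under the any-of-five rule at correlation 0 has the closed form 1 − 0.95⁵ = 0.226.

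| Correlation (within / otherwise) | Error, any of five | Power, all five (SD 40% on the contrast) |
|---|---|---|
| 0.7 / 0.3 | 0.193 | 0.472 |
| 0.8 / 0.3 | 0.184 | 0.488 |
| 0.7 / 0.5 | 0.176 | 0.523 |
| 0.8 / 0.5 | 0.167 | 0.534 |
| 0 / 0 | 0.226 | 0.319 |
| 0.9 / 0.9 | 0.102 | 0.677 |

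**4. If 40% is a per-visit SD.** The SD of a mean of k visits with within-patient correlation r is 40 × √((1 + (k − 1)r)/k).

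- k = 4: 40 × √0.625 = 31.6% at r = 0.5; 40 × √0.775 = 35.2% at r = 0.7.
- k = 3 (QoR-15): 32.7% and 35.8%.

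Single-scale power is then 0.94 or 0.89 (four visits) and 0.93 or 0.88 (three visits). Power for all five is 0.79 to 0.82 at r = 0.5 and 0.65 to 0.69 at r = 0.7 (extremes 0.73 and 0.88; 0.54 and 0.80). This assumes that the 22.5% effect is constant over post-dose visits, that baseline is left out of the average, and that VAS has four assessments.

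**5. Interim look.** The plan gives no interim level. If 0.05 is used at both 50 and 100 patients (information 0.5 and 1), error is 0.083 for one scale and 0.26 to 0.30 for any of five (0.35 at correlation 0, 0.16 at 0.9).

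**6. Check of the remedies** (normal approximation).

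- Classical O'Brien-Fleming at overall 0.05 has z limits 2.797 and 1.977, that is p < 0.0052 and p < 0.048. Single-scale power is 0.800 against 0.803 with one look.
- Applied to each of five scales without a multiplicity rule, that boundary still leaves any-of-five error at 0.17 to 0.19.
- At overall 0.01 per scale the limits are z 3.648 and 2.580, that is p < 0.00026 and p < 0.0099. Any-of-five error over both looks is then at most 0.049.
- With all five required, the 0.05 boundary gives power 0.476 to 0.542, against 0.484 to 0.549 with one look.

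**The case against.** The strongest reply is that the plan never says one scale is enough. Its only success wording is plural and can be read as requiring all five, in which case there is no inflation across scales. That is right, so 0.17 to 0.19 is the consequence of one reading and not the plan's established error rate. But the wording appears only in the interim stopping rule, does not say all, and gives no level. On that reading the stated 0.8 still has no support for the joint requirement.

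A second reply is that the five scales are correlated. They probably are, but even at 0.9 the any-of-five error is about twice 0.05.

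A third is that the per-visit figures in step 4 depend on choices the plan leaves open. This stands. If baseline enters the treatment main effect as an ordinary visit for BDI, MADRS and QoR-15, power for all five falls to about 0.56 to 0.61 at within-patient correlation 0.5 and 0.41 to 0.47 at 0.7. The number of VAS assessments also varies with the day of discharge. Those figures show how far power moves with unstated choices, and none of them is an estimate for this trial.

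Two limits on scope are also fair. The interim error of 0.083 would exist with a single primary scale, so it is a separate effect that adds to this one. And the choice of scale belongs to the investigators: the antidepressant basis of the sample size points to a mood scale, but the objectives and hypothesis name pain too.

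Nor can the trial be excused as exploratory. It states a null hypothesis, an error rate, a power and an early stopping rule, and applies the word exploratory only to the serum markers and the logistic regression.

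**Conclusion.** The concern holds and must be fixed. The sample size arithmetic is correct for one outcome, but the plan does not say which outcome that is, and the stated error and power are not shown to apply to the five-scale primary set.

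Under an any-of-five rule the final-analysis error is about 0.17 to 0.19 instead of 0.05. Under an all-five rule error is not inflated across scales, and power is about 0.47 to 0.53 if 40% is the SD of the analysed contrast; it can reach 0.8 only under particular assumptions about visits and correlations. These ranges rest on assumed correlations. The absence of a rule does not depend on them.

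**What to change.** Before any unblinded outcome analysis:

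1. Name one primary scale and one contrast, for example the repeated-measures treatment effect or a single day, and state whether the 40% SD is per visit or of that contrast. BDI or MADRS would match the mood part of Specific aim 1 and the basis of the sample size. With SD 40% on the contrast, 50 per arm and power of about 0.80 stand.
2. Make the other four scales secondary, tested only if the primary succeeds: either in fixed order at the same look-specific limits, or by Holm with limits recomputed for the reduced alpha.
3. Define the interim condition as the primary scale crossing a group-sequential boundary, for example O'Brien-Fleming with p < 0.0052 at 50 patients and p < 0.048 at 100.

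If all five stay primary, state which rule applies and its limits at both looks, then restate power or detectable difference from stated SDs and correlations:

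- **Any of five:** Holm, with the strictest step at overall alpha 0.01 per scale, for example p < 0.00026 at 50 and p < 0.0099 at 100.
- **All five:** every scale below 0.0052 at 50, or every scale below 0.048 at 100.

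**Cost.** With one primary scale the change is wording only: four scales lose primary status, no patients are added, and the boundary costs about 0.3 percentage points of power. With all five required, the boundary costs 0.5 to 1.0 points on top of the low joint power. With Holm, power for a given scale at its strictest step (single look) drops from 0.795 to 0.575. Keeping 50 per arm then means a detectable difference of 8.0 × (2.576 + 0.842) = 27.3%; restoring 80% power for 22.5% would need 74 to 76 per arm.

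The documents do not show whether the 50-patient look has taken place. If it has, report the rule that was used.
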